Table 9: Guidelines for Interruption and Restarting of Treatment Applications if Adverse Event Is Deemed Related to the Study Cream	45
Table 10: Investigator's Global Assessment	54
Table 11: Required Laboratory Analytes.....	61
Table 12: Populations for Analysis.....	72

LIST OF FIGURES

Figure 1: Study Design Schema	13
Figure 2: Study INCB 18424-303 and Study INCB 18424-304: Proportions of Participants Who Achieved IGA-TS	24
Figure 3: Study INCB 18424-303 and Study INCB 18424-304: Change From Baseline in Daily Itch NRS Score	25
Figure 4: Box Plots of Steady-State Plasma Concentrations Overlaid With Mean Values (Log ₁₀ Scale).....	26

LIST OF ABBREVIATIONS

Abbreviations and Special Terms	Definition
IL	interleukin
IRB	institutional review board
IRT	interactive response technology
ITT	intent-to-treat
JAK	Janus kinase
LLN	lower limit of normal
LTS	long-term safety
MedDRA	Medical Dictionary for Regulatory Activities
NRS	Numerical Rating Scale
P1NP	procollagen type 1 N-terminal propeptide
PD	pharmacodynamic
PDE4	phosphodiesterase 4
[REDACTED]	[REDACTED]
PK	pharmacokinetics
[REDACTED]	[REDACTED]
PP	per protocol
[REDACTED]	[REDACTED]
[REDACTED]	[REDACTED]
[REDACTED]	[REDACTED]
RNA	ribonucleic acid
SAE	serious adverse event
SAP	statistical analysis plan
SoA	schedule of activities
SOP	standard operating procedure
SPF	sun protection factor
Study cream	This term refers to Incyte medicinal investigational product(s) or matching placebo(s) used for this study.
Study treatment	This term refers to all medications that the participant is required to receive as part of this study.
TEAE	treatment-emergent adverse event
ULN	upper limit of normal
UV	ultraviolet
[REDACTED]	[REDACTED]
VC	vehicle-controlled

1. PROTOCOL SUMMARY

Protocol Title:

Topical **Ruxolitinib** Evaluation in **Atopic Dermatitis** Study **3** (TRuE-AD3)

A Phase 3, Double-Blind, Randomized, Vehicle-Controlled, Efficacy and Safety Study of Ruxolitinib Cream Followed by a Long-Term Safety Extension Period in Children (Ages \geq 2 Years to < 12 Years) With Atopic Dermatitis

Protocol Number: INCB 18424-305

Objectives and Endpoints:

[Table 1](#) presents the primary and key secondary objectives and endpoints.

Table 1: Primary and Key Secondary Objectives and Endpoints

Objectives	Endpoints
Primary	
To establish the efficacy of ruxolitinib cream in participants with AD.	Proportion of participants who achieve IGA-TS at Week 8.
Key Secondary	
To further assess the treatment effects of ruxolitinib cream.	Proportion of participants with a \geq 4-point improvement in Itch NRS score from baseline to Week 8. Proportion of participants with a \geq 4-point improvement in Itch NRS score from baseline to Day 7 (Week 1). Proportion of participants with a \geq 4-point improvement in Itch NRS score from baseline to Day 3.

Overall Design:

[Table 2](#) presents the key study design elements. Further study details are presented after the table.

Table 2: Key Study Design Elements

Study Phase	Phase 3
Clinical Indication	Atopic dermatitis
Population	Children aged \geq 2 years to $<$ 12 years (with at least 40% of participants ages \geq 2 years to 6 years) who have been diagnosed with AD for at least 3 months, have an IGA score of 2 to 3, and have %BSA involvement (excluding the scalp) of 3% to 20%.
Number of Participants	Approximately 315 participants will be randomized 2:2:1 to 1 of 3 treatment groups (ruxolitinib cream 0.75% BID [n = 126], ruxolitinib cream 1.5% BID [n = 126], or vehicle cream BID [n = 63]). The study will be conducted at approximately 60 sites in the United States and Canada.
Study Design	Randomized (2:2:1), double-blind, VC period (8 weeks) followed by an LTS period (44 weeks) and a 30-day safety follow-up period after the last application of study cream. In the LTS period, participants initially randomized to vehicle cream will be rerandomized (1:1) in a blinded manner to ruxolitinib cream 0.75% or 1.5%, and participants initially randomized to an active treatment group will continue in the same treatment group.
Estimated Duration of Study Participation	Screening period: up to 28 (+ 7) days VC period: approximately 8 weeks LTS period: approximately 44 weeks Safety follow-up period: 30 days after the last application of study treatment or last study visit Total: up to approximately 61 weeks
Data Safety Monitoring Board/Data Monitoring Committee	No
Coordinating Principal Investigator	[REDACTED], MD

Treatment Groups and Duration:

Male and female children aged \geq 2 years to $<$ 12 years who have been diagnosed with AD for at least 3 months and have an IGA score of 2 to 3 and %BSA involvement (excluding the scalp) of 3% to 20% will be eligible to participate in the study. Participants who have met all of the inclusion criteria during the screening period (up to 28 days or up to 35 days for participants taking prior medications that require a 4-week washout period [see Section 5.2, Exclusion Criterion 6b]) will be enrolled (randomized 2:2:1) and receive blinded treatment with ruxolitinib 0.75% cream BID, ruxolitinib 1.5% cream BID, or vehicle cream for a total treatment duration of 8 weeks during the VC period of the study.

[figure not shown]
Participants who complete the Week 8 assessments with no additional safety concerns will continue into the 44-week LTS period with the same treatment regimen, except those initially treated with vehicle cream will be rerandomized (1:1) in a blinded manner to 1 of the 2 active

treatment groups (ruxolitinib cream 0.75% or 1.5% BID). The IGA score required for participants to enter the LTS period is 0 to 4, and participants must have a %BSA in the range of 0% to 20% (excluding the scalp).

Following the end of treatment (Week 52/EOT or ET), all participants will have a safety follow-up visit 30 days later (or 30 days after the last application of study treatment if the Week 52/EOT or ET visit was not performed).

Figure 1 presents the study design schema, and **Table 3** (VC period) and **Table 4** (LTS period) present the SoA. Adherence to the study design requirements, including those specified in the SoA, is essential and required for study conduct.

Figure 1: Study Design Schema

* At Week 8 (LTS baseline), participants initially on vehicle during the VC period will be rerandomized to either ruxolitinib 1.5% or 0.75% cream BID. Participants initially randomized to either ruxolitinib 0.75% or 1.5% BID will continue their treatment through the LTS period.

** Treatment is ceased 3 days after clearing of AD lesions. Treatment is restarted if AD lesions recur. There is no limit on the number of treatment cycles during the 44-week LTS.

Table 3: Schedule of Activities: Vehicle-Controlled Period

Visit Day (Range)	Screening	VC Period				Notes and Protocol Section
	Days -28 (+ 7 ^a) to -1	Day 1/ Baseline	Wk 2 (± 3 d)	Wk 4 (± 3 d)	Wk 8 ^b /ET (± 3 d)	
Administrative procedures						
Informed consent/assent	X					Section 8.1.1.
Contact IRT	X	X	X	X	X	Section 8.1.3.
Inclusion/exclusion criteria	X	X				Section 5.
Demography and general medical history	X*					Section 8.1.5.1. *Height and weight of both parents, if available, should be obtained and entered into the EDC.
Relevant AD medical and treatment history	X					Section 8.1.5.2.
Collect/obtain growth measurements for the year prior to study entry	X*	X*				Section 8.4.3. *Collected at either screening or baseline. A reasonable effort must be made to collect and document measurements prior to baseline. If unable to obtain, the reason should be documented.
Prior/concomitant medications and procedures	X	X	X	X	X	Section 6.6.
Apply study cream at site		X	X	X	X*	Section 6.1; at each visit (except for the Week 8 visit if IGA is 0), starting at Day 1, the participant should apply the first (morning) application under direct site staff supervision to all areas identified at Day 1, even if the AD lesion is cleared or disappeared. *Not applicable to the ET visit.
Weigh and dispense study cream; dispense diary cards		X	X	X	X*	Section 6.1 and Section 8.1.4. * Not applicable to the Week 8 visit if IGA score = 0 or to the ET visit.
Collect and weigh study cream; collect diary cards			X	X	X	Section 6.1.
Assess compliance			X	X	X	Section 6.4.
Safety assessments						
AE assessment	X	X	X	X	X	Section 8.4.1.
Comprehensive physical examination	X				X*	Section 8.4.2.1. *For the ET visit only.

Table 3: Schedule of Activities: Vehicle-Controlled Period (Continued)

Visit Day (Range)	Screening	VC Period				Notes and Protocol Section
	Days -28 (+ 7 ^a) to -1	Day 1/ Baseline	Wk 2 (± 3 d)	Wk 4 (± 3 d)	Wk 8 ^b /ET (± 3 d)	
Safety assessments (continued)						
Targeted physical examination*		X	X	X	X†	
Section 8.4.2.2.
 
*Conducted only when indicated by symptoms reported by participant (ie, AEs or other findings); clinically significant abnormalities (in the investigator's judgment) are to be reported as AEs.
 
†Not done for the ET visit.

Height and weight		X			X	Section 8.4.3; height should be measured with a stadiometer.
Vital signs	X	X	X	X	X	Section 8.4.3; vital signs are taken before blood sampling and other procedures.
Efficacy assessments						
Evaluate %BSA affected by AD (excluding skin dryness)	X	X	X	X	X*	
Section 8.2.2; evaluate %BSA (excluding the scalp) affected by active AD lesions using the handprint method.
 
*At Week 8, the %BSA range is 0% to ≤ 20% for the LTS period.

Target lesion identification	X	X*				
Section 8.2.3; the longest diameter and the span perpendicular to the longest diameter will be measured in centimeters.
 
*For photography participants, a lesion of ≥ 5 cm² (target lesion) is to be identified at screening and confirmed at the baseline visit (excluding the hands, feet, and genitalia).

Photography (target lesion and regional body area)*		X	X	X	X	
Section 8.2.4; photography of the target lesion area identified at Day 1/baseline even if the lesion has cleared.
 
*Performed only for photography participants at selected sites.

IGA	X	X	X	X	X*	
Section 8.2.5.
 
*At Week 8, the IGA range is 0 to 4 for the LTS period.

EASI	X	X	X	X	X	Section 8.2.6; evaluate EASI in 4 regions (head/neck, upper limbs, trunk, and lower limbs) and overall.
Itch NRS	eDiary is completed each evening from screening through the last application of study cream during the VC period (night prior to Week 8 visit).				
Section 8.2.7; baseline itch (defined as the average of at least 4 of the 7 days directly before Day 1) must be NRS ≥ 4.
 
Note: Itch is collected from participants ≥ 6 years of age.
	

Table 3: Schedule of Activities: Vehicle-Controlled Period (Continued)

Visit Day (Range)	Screening	VC Period				Notes and Protocol Section	
	Days -28 (+ 7 ^a) to -1	Day 1/ Baseline	Wk 2 (± 3 d)	Wk 4 (± 3 d)	Wk 8 ^b /ET (± 3 d)		
Laboratory assessments					Blood draws for clinical laboratory tests must be performed before the in-clinic study cream application. Use of a topical anesthetic prior to blood draw is recommended.		
Serum chemistries	X	X*	X		X	Section 8.4.4. *Day 1 testing will be performed only if the interval between this visit and the screening visit is > 2 weeks.	
Hematology	X	X*	X		X	Section 8.4.4. *Day 1 testing will be performed only if the interval between this visit and the screening visit is > 2 weeks.	
Serology	X*					Section 8.4.4.3. *HIV antibody.	
Pregnancy testing	X	X*			X	Section 8.4.4.2; at the indicated visits, only female participants who have reached menarche will undergo a urine pregnancy test. A positive urine test must be confirmed by a serum test. *Day 1 testing will be performed only if the interval between this visit and screening is > 2 weeks.	

Table 3: Schedule of Activities: Vehicle-Controlled Period (Continued)

Visit Day (Range)	Screening	VC Period				Notes and Protocol Section
	Days -28 (+ 7 ^a) to -1	Day 1/ Baseline	Wk 2 (± 3 d)	Wk 4 (± 3 d)	Wk 8 ^b /ET (± 3 d)	

Note: Unscheduled visits may occur at any time at the investigator's discretion, and appropriate clinical and laboratory tests may be performed as clinically indicated.

^a For prior medications that require a 4-week washout period (see Section 5.2, Exclusion Criterion 6b), a 35-day screening period is allowed.

^b Week 8 is the baseline for participants eligible to continue in the LTS period (IGA score = 0-4 and BSA = 0%-20%).

Table 4: Schedule of Activities: Long-Term Safety Period

Visit Day (Range)	LTS Period					Unscheduled Visit	Safety Follow-Up 30 (+ 7) Days After Last Study Cream Application ^a	Notes and Protocol Section
	Wk 12 (± 7 d)	Wk 16, 20, and 24 (± 7 d)	Wk 28, 32, and 36 (± 7 d)	Wk 40, 44, and 48 (± 7 d)	Wk 52/ EOT/ET (± 7 d)			
Administrative procedures								
Contact IRT	X	X	X	X	X	X	X	Section 8.1.3.
Prior/concomitant medications and procedures	X	X	X	X	X	X	X	Section 6.6.
Apply study cream at site	X	X	X	X				Section 6.1; only for participants with active AD lesions at time of visit; apply the first (morning) application under direct site staff supervision.
Weigh and dispense study cream; dispense diary cards	X	X	X	X				Section 6.1 and Section 8.1.4.
Collect and weigh study cream; collect diary cards	X	X	X	X	X			Section 6.1.
Record start and end dates of treatment cycle(s)	X	X	X	X	X			Section 6.1; the start/end date will have been recorded by the participant. The end date should be 3 days after lesions clear; however, if this 3-day window is during a study visit and IGA score = 0, stop treatment and record the date of the study visit as the treatment cycle end date.
Assess compliance	X	X	X	X	X			Section 6.4.
Safety assessments								
AE assessments	X	X	X	X	X	X	X	Section 8.4.1.
Comprehensive physical examination					X			Section 8.4.2.1.
Targeted physical examination	X	X	X	X		X	X	Section 8.4.2.2; conducted only when indicated by symptoms reported by participant (AEs or other findings); clinically significant abnormalities (in the investigator's judgment) are to be reported as AEs.

Table 4: Schedule of Activities: Long-Term Safety Period (Continued)

Visit Day (Range)	LTS Period					Unscheduled Visit	Safety Follow-Up 30 (+ 7) Days After Last Study Cream Application ^a	Notes and Protocol Section
	Wk 12 (± 7 d)	Wk 16, 20, and 24 (± 7 d)	Wk 28, 32, and 36 (± 7 d)	Wk 40, 44, and 48 (± 7 d)	Wk 52/ EOT/ET (± 7 d)			
Safety assessments (continued)								
Height and weight		X*			X			Section 8.4.3; height should be measured with a stadiometer. *Only at Week 24.
Vital signs	X	X	X	X	X	X	X	Section 8.4.3; vital signs are taken before blood sampling and other procedures.
Disease severity assessments								
Evaluate %BSA affected by active AD lesions	X	X	X	X	X	X	X	Section 8.2.2; evaluate %BSA (excluding the scalp) affected by active AD lesions using the handprint method.
IGA	X	X	X	X	X	X	X	Section 8.2.5.

Table 4: Schedule of Activities: Long-Term Safety Period (Continued)

Visit Day (Range)	LTS Period					Unscheduled Visit	Safety Follow-Up 30 (+ 7) Days After Last Study Cream Application ^a	Notes and Protocol Section
	Wk 12 (± 7 d)	Wk 16, 20, and 24 (± 7 d)	Wk 28, 32, and 36 (± 7 d)	Wk 40, 44, and 48 (± 7 d)	Wk 52/ EOT/ET (± 7 d)			
Laboratory assessments								Blood draws for clinical laboratory tests must be performed before the in-clinic study cream application.
Serum chemistries	X	X*	X*	X*	X	X	X	Section 8.4.4. *Only at Weeks 16, 24, 32, 40, and 48.
Hematology	X	X*	X*	X*	X	X	X	Section 8.4.4. *Only at Weeks 16, 24, 32, 40, and 48.
Pregnancy testing		X*	X*	X*			X	Section 8.4.4.2; at the indicated visits, only female participants who have reached menarche will have urine pregnancy test. A positive urine test must be confirmed by a serum test. *Only at Weeks 16, 24, 32, 40, and 48.

Note: Unscheduled visits may occur at any time at the investigator's discretion, and appropriate clinical and laboratory tests may be performed as clinically indicated.

^a Except for participants who have been in an observation/no treatment cycle with a total IGA score of 0 (clear) from Week 48 or earlier until Week 52; such participants should complete the safety follow-up and Week 52/EOT visits together. In practice, this would mean conducting all Week 52/EOT visit assessments plus the pregnancy test at the Week 52/EOT visit.

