4. STUDY DESIGN

4.1. Overall Design

This is a randomized, double-blind, VC study with an LTS period in pediatric participants with AD eligible for topical therapy, to be conducted at approximately 60 sites in the United States and Canada. For participants who meet all study inclusion criteria and none of the exclusion criteria, study cream will be assigned at the Day 1/baseline visit. Participants will be randomized 2:2:1 to blinded treatment with ruxolitinib cream 0.75% BID, ruxolitinib cream 1.5% BID, or vehicle cream BID, with stratification by baseline IGA score and age. Enrollment will be capped such that no more than approximately 25% of randomized participants have a baseline IGA score of 2. At least 40% of the overall study population will consist of children aged \geq 2 years to 6 years.

During the 8-week VC period, participants will apply study treatment BID to all areas identified for treatment at the Day 1/baseline visit even if the AD begins to improve and lesions decrease in size. Note: Throughout this protocol, the term "participant" refers either to the participants themselves or, in the case of younger children, their parent or legal guardian.

At Week 8, efficacy (the primary endpoint of the study) will be evaluated as the proportion of participants achieving treatment success (IGA score of 0 or 1 with \geq 2-grade improvement from baseline).

Participants who complete Week 8 assessments with no additional safety concerns will continue into the 44-week LTS period with the same treatment regimen, except those initially randomized to vehicle cream will be rerandomized (1:1) in a blinded manner to 1 of the 2 active treatment groups (ruxolitinib cream 0.75% or 1.5% BID). The IGA score required for participants to enter the LTS period is 0 to 4, and participants must have a %BSA in the range of 0% to 20% (excluding the scalp).

During the LTS period, participants will have study visits every 4 weeks until the end of the study (52 weeks total). At each of these visits, including Week 8 (baseline visit for the LTS period), the participant's AD lesions will be evaluated by the investigator to determine whether the participant requires continuation of treatment or should (re)enter an observation/no treatment cycle. If the IGA score is \geq 1, the participant will start or continue active treatment with ruxolitinib cream (0.75% or 1.5%) BID. If the IGA score is 0 (clear), the participant will (re)enter an observation/no treatment cycle.

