During the LTS period (ie, starting at the Week 8 visit), participants will self-evaluate the recurrence of AD and will treat areas of the skin with active AD changes only (not to exceed 20% BSA). If AD lesions clear between study visits, participants will stop treatment applications 3 days after the lesions have disappeared and record the dates of these events in their diaries. Similarly, those participants whose AD lesions recurred and who were previously in an observation/no treatment cycle will restart treatment at home at the first sign of recurrence and record the date of the new treatment cycle. All cycles of treatment will be captured in the study database with their beginning and end dates.

Throughout the study (VC period or LTS period), participants who develop new or expanded areas of AD may treat these additional areas with approval by the investigator as long as the total treated BSA does not exceed 20% and there are no safety concerns regarding the additional

application of study cream. Approval to treat additional areas may occur via telephone, although the investigator, at his/her discretion, may ask the participant to return for an unscheduled visit. This is a close reflection of the clinical practice of managing AD in the outpatient setting.

If the participant does not have a response during the LTS period (defined as no change/improvement in either %BSA or IGA score when treated continuously for 8 weeks during the LTS period), the participant must be discontinued from study treatment and an ET visit performed.

Throughout the study, participants will be assessed for safety and tolerability by monitoring the type, frequency, and severity of AEs; performing physical examinations; measuring vital signs, height, and weight; and conducting clinical and laboratory assessments as outlined in the SoA (see [Table 3](#) [VC period] and [Table 4](#) [LTS period]). Additional disease severity assessments, including PROs, will be conducted as outlined in the SoA (see [Table 3](#) and [Table 4](#)).

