If there are new areas to be treated, including expansion of existing areas or development of new areas, after consultation with the investigator, study cream should be applied to these areas in addition to the areas identified at the baseline visit (up to 20% BSA) for the remainder of the VC period, and the percentage of BSA to be treated will be recalculated and increased. This new estimate will be entered into the IRT system to calculate the number of tubes of study cream to be dispensed. Approval to treat these additional areas may occur via telephone, although the investigator, at their discretion, may ask the participant to return for an unscheduled visit. This is a close reflection of the clinical practice of managing AD in the outpatient setting. Participants

whose additional new areas to be treated in addition to the areas identified at the baseline visit exceed 20% BSA should be discontinued from study treatment and complete the EOT assessments.

During the LTS period starting at the Week 8 visit, participants will have study visits every 4 weeks until the end of the study (44 weeks total). At those visits, AD lesions will be evaluated by the investigator to confirm whether the participant still requires continuation of therapy (IGA score ≥ 1) or can otherwise (re)enter the observation/no treatment cycle (IGA score = 0). During this period, only areas with active disease need to be treated. Participants who develop new or expanded areas of AD may treat these additional areas with approval by the investigator as long as the total treated BSA does not exceed 20% and there are no safety concerns regarding the additional application of study cream. At Week 8, each participant will receive a prespecified number of tubes of study cream corresponding to a lower %BSA affected (up to 5%) or higher number of tubes corresponding to their affected %BSA ($> 5\%$). This new estimate will be entered into the IRT system to calculate the number of tubes of study cream to be dispensed.

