The start and end dates of treatment applications will be captured by the participant. Once the lesions clear, participants should continue to apply study cream for an additional 3 days to the areas of the body where lesions were last present before discontinuing treatment. If this 3-day window is during a study visit and the IGA score is 0, as assessed by the investigator, treatment is to be stopped. The date of the study visit will be recorded as the treatment cycle end date. If a lesion recurs, then treatment should be resumed at the first sign of recurrence.

At any time during the LTS period, if a participant's new areas to be treated in addition to the areas identified at the previous visit exceed 20% BSA, then the participant should be discontinued from study treatment and complete the EOT assessments.

No study treatment adjustments are allowed except for temporary drug discontinuation, if needed (eg, for management of an AE; see Section 6.5).

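### Table 3 withholds cream and diary cards at Week 8 from a child with IGA 0, while Section 6.1 supplies everyone; under Table 3 the home restart has no scheduled supply until Week 12

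*Protocol*

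**What the plan says.** Four pieces of current protocol text bear on a child with IGA 0 at Week 8.

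- **Table 3, dispensing row.** Cream and diary cards are given out at Day 1 and Weeks 2, 4 and 8, with the note "Not applicable to the Week 8 visit if IGA score = 0 or to the ET visit".
- **Table 3, collection row.** "Collect and weigh study cream; collect diary cards" is marked at Weeks 2, 4 and 8, with no exception for IGA 0.
- **Section 6.1, Week 8 supply.** "At Week 8, each participant will receive a prespecified number of tubes of study cream". There are two tiers, the lower covering up to 5% BSA. No exception is made for IGA 0, and a child with 0% BSA fits the lower tier.
- **Sections 4.1 and 6.1, re-treatment.** Section 4.1 counts Week 8 among the visits at which IGA decides treatment: "If the IGA score is 0 (clear), the participant will (re)enter an observation/no treatment cycle". A child in such a cycle whose lesions return "will restart treatment at home at the first sign of recurrence and record the date of the new treatment cycle". Section 6.1 repeats the instruction: "If a lesion recurs, then treatment should be resumed at the first sign of recurrence".

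Table 4 handles the same situation differently from Week 12 on. Only on-site application is limited to children with active lesions; dispensing at Weeks 12 to 48 carries no such limit. At unscheduled visits, Table 4 marks IRT contact but not dispensing.

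**The concern.** A site cannot follow both Table 3 and Section 6.1 for a child who is clear at Week 8. Section 1 of the protocol makes adherence to the schedule of activities mandatory, so the table note cannot be set aside as guidance.

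Under Table 3, that child hands back cream and diary and goes home with neither, yet is told to restart at home as soon as a lesion returns. A vehicle child who is clear has just been rerandomized to active cream and would have no scheduled supply of it. Section 6.6.3 rules out other topical AD treatments apart from bland emollients, so little else is available in the meantime.

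Two things are at stake. One is prompt re-treatment of a young child. The other is the dating of the new treatment cycle. Section 2.3.1 says the long-term period will show how long the effect lasts after treatment stops at clearance. For children clear at Week 8, the first such interval starts exactly where supply is in doubt.

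**Working it through.** **Does the rule reach these children?** IGA 0 to 4 and BSA 0% to 20% are accepted for entry to the long-term period (Section 4.1), so a clear child continues. The IGA rule applies at Week 8, so that child starts an observation cycle there. Cream from the vehicle-controlled period does not help: Table 3 collects it, and for a vehicle child it would be the wrong product.

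**Length of the interval between scheduled dispensings.**

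Inputs:
- Long-term visits are every 4 weeks (Section 4.1).
- Week 8 target is Day 57 (SAP Section 6.3), window ±3 days (Table 3).
- Week 12 window is ±7 days (Table 4).
- Under pandemic rules the Week 8 window is ±7 days (Appendix C).

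Formula: interval = day of the Week 12 visit − day of the Week 8 visit.

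1. The plan's own spacing: (12 − 8) × 7 = 28 days. With Week 12 at 57 + 28 = Day 85, 85 − 57 = 28, which reproduces it.
2. Week 8 falls on Days 54 to 60 and Week 12 on Days 78 to 92.
3. Shortest: 78 − 60 = 18 days. Longest: 92 − 54 = 38 days.
4. With the Appendix C window, Week 8 falls on Days 50 to 64. Shortest: 78 − 64 = 14 days. Longest: 92 − 50 = 42 days.
5. If Section 6.1 is followed, cream is in hand from Week 8 and the interval is 0 days.

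**From supply interval to delay.** Let r be the days from the Week 8 visit to recurrence and s the days to resupply, with s no larger than the interval above. Re-treatment is delayed by s − r. At nominal visits with no earlier resupply this is 28 − r, which approaches 28 only if the lesion returns almost at once. A child without recurrence has no delay.

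**Effect on the recorded dates.** When treatment stops at a visit with IGA 0 inside the three-day window after clearance, Section 6.1 says: "The date of the study visit will be recorded as the treatment cycle end date". I assume the same anchor for treatment that ends at Week 8. The next date the participant is visibly asked to record is the start of the new cycle; no separate recurrence-date field is visible. The recorded off-treatment interval is then s instead of r, too long by the same s − r.

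**The case against.** **The table note may simply be a specific exception to a general sentence.** That reading would settle which text governs, and the exception looks deliberate. As background only, Appendix F records under Amendment 4 that it was extended to dispensing, though the reason given mentions only application. But this reading does not supply the home restart, and nothing explains why a child clear at Week 12 is supplied while one clear at Week 8 is not.

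**Re-treatment before Week 12 is not ruled out.** A reader might infer that it is impossible. The documents do not support that. Section 8.7 allows unscheduled visits whenever medically warranted, including for new areas of AD, and Table 4 marks IRT contact at them. The blank dispensing cell does not forbid supply. This objection stands, and it limits the point to a restart at home from scheduled supply. A clinic visit is a partial route and not the restart that Section 4.1 describes.

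**The 28 days is not a treatment delay.** A reader might take it as 28 days untreated. It is a supply interval and only bounds the delay from above. This also stands.

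**The IRT may already follow Section 6.1.** Tube numbers come from the IRT, whose rule for this case is not in the documents. If it follows Section 6.1, no child goes without cream. That children went unsupplied, or that sites acted differently, is therefore possible but not shown. What is certain is the conflict in the text.

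**Conclusion.** The point holds as a minor internal inconsistency. Table 3 and Section 6.1 disagree on Week 8 dispensing at IGA 0. Under Table 3, the home restart has no scheduled supply for 28 days nominally, or 18 to 38 days across the standard windows (14 to 42 days where the pandemic window applies).

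This rests on Table 3 being followed as written and on the Week 12 visit taking place within its window. The bound on delay is reached only if recurrence is almost immediate and no unscheduled resupply occurs. The number of children affected cannot be estimated: the documents give neither an IGA 0 rate at Week 8 nor a recurrence rate before Week 12.

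A reader might infer that cycle dates are safe because the end date is fixed by the visit. They are not: the start of the new cycle stands in for recurrence and would be late, which lengthens the apparent duration of effect. A reader might also infer a threat to the efficacy conclusions. There is none. The Week 8 primary and key secondary tests use data collected up to that visit, and Type I error and sample size are unaffected. The consequence is confined to descriptive long-term data, and the visible SAP plans no analysis of cycle length or time to recurrence.

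**What to change.** - Change the Table 3 dispensing note so that it excludes only the ET visit.
- Keep the Week 8 IGA 0 exception for on-site application only, as Table 4 does from Week 12.
- Dispense lower-tier tubes and a diary card at Week 8 to every participant entering the long-term period.
- Set the IRT rule to match.

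Adding the exception to Section 6.1 instead would remove the textual conflict but leave the home restart without scheduled supply before Week 12.

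The cost is a small protocol amendment, with the IRB/IEC and health authority approval that Section 11.1 requires, a check of the IRT, and a few extra tubes and diary cards. No visit, procedure or data field is added.
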